### **3.3.3 Exclusion criteria**

Any of the following is regarded as a criterion for exclusion from the study:

1. Patients who exhibit total resolution of all signs and symptoms of GERD during the initial 8 hour video assessment.
2. Use of any pharmacological antireflux therapy (other than study drug) within 72 hours prior to any pH/impedance monitoring. Antacids may be used if it is required during the study as "rescue therapy", but are not allowed to be taken  $\pm$  1 hour to administration of the investigational product and also not 4 hours before and throughout the pH-impedance monitoring at baseline and the final study day.
3. Patients with a history or a current need for resectional or reconstructive surgery of the gastrointestinal tract (esophagus, stomach, duodenum or jejunum).
4. Patients with any condition that may require surgery during the course of the study.
5. Patients who must remain on any of the following concomitant medications during the course of the study: bismuth-containing products, barbiturates, anti-convulsants, warfarin, narcotics, antineoplastic agents, H2 receptor antagonists, sucralfate, anti-emetics, pro-motility drugs (eg, cisapride, metoclopramide, macrolide antibiotics such as erythromycin). Use of topical erythromycin is permissible. However, occasional use of restricted medications, when medically indicated after enrollment, is permissible at the discretion of the investigator. If any restricted medication is used, the name of the medication and the reason for taking it should be recorded on the eCRF.
6. Patients with the following diseases/conditions: active gastrointestinal bleed, allergic gastroenteropathies, eosinophilic gastroenteritis, bleeding disorders, active

seizure disorder, on-going treatment for seizure disorder, acute pancreatitis or meningitis.

7. Patients with acute respiratory distress within 72 hours prior to enrollment or the likelihood of acute or worsening respiratory distress during the course of the study.
8. Patients who are febrile per NICU standards on the day of randomization.
9. Patients with any acute or chronic illness that, in the opinion of the investigator, would place the patient at risk because of their participation in the study *or* potentially confound the study data by including the patient. Conditions that should be considered for exclusion (however, exclusion is neither required nor limited to): acute pneumonia, acute respiratory syncytial virus, recent trauma, known or suspected abuse or neglect, severe malabsorption, fever of unknown origin, or any unstable or severe renal, hepatic, cardiac, pulmonary, metabolic, or congenital problems that could put the child at risk by participating in the study. Severe fetal alcohol syndrome and newborn drug withdrawal syndrome should be considered for exclusion. The decision to exclude a patient from study participation in these cases will be made by the investigator and/or AstraZeneca physician based on the severity of the condition and potential risk to the patient.
10. Patients with abnormal screening laboratory values will be excluded only if the investigator and/or sponsor determine the abnormalities to be unexplained or clinically significant in a way that would put the patient at risk from study participation.
11. Known or suspected hypersensitivity to any esomeprazole formulation or substituted benzimidazoles.
12. Patients who have used any other investigational compound prior to the screening visit. Patients who have used investigational devices or products that are not systemically absorbed prior to the screening visit should be discussed with the sponsor on a case-by-case basis prior to study enrollment.
13. Patients who have any condition that, in the judgment of the investigator, would make performance of any of the study procedures unsafe, or which would make it unlikely that the patient would complete the study and all study procedures to final study day.
14. Need for switch of feeding route during study or change in the type of feeding must be carefully decided on a case-by-case basis.
15. Previous enrollment or randomization of treatment in the present study.

### **3.3.4 Restrictions**

For drugs not allowed during the study, refer to exclusion criteria no. 4. Food thickeners can be used in the 72-hour period up to four hours prior to the pH/impedance monitoring. Antacids may be used if required during the study as “rescue therapy”, but are not allowed to be taken  $\pm$  1 hour to administration of the investigational product and also not 4 hours before and throughout the pH-impedance monitoring at baseline and the final study day. Occasional use of restricted medications, when medically indicated after enrollment, is permissible at the discretion of the investigator. If any restricted medication is used, the name of the medication and the reason for taking it should be recorded on the eCRF.

Due to the medical, procedural and other logistical limitations inherent to this patient population (neonates and premature babies), every effort will be made to follow the protocol’s designated procedures and variable measurements. However, at the investigator’s discretion and with the sponsor’s approval, some of these may need to be waived or adjusted based on patient size and medical condition without constituting a protocol deviation. Other standard of care procedures that a patient may require during the study will be documented at the time of performance.

### **3.3.5 Discontinuation of patients from treatment or assessment**

#### **3.3.5.1 Criteria for discontinuation**

Patients may be discontinued from study treatment and assessments at any time. Specific reasons for discontinuing a patient from this study are:

- Voluntary discontinuation by the patient’s parent or guardian who are at any time free to discontinue their participation in the study, without prejudice to further treatment.
- Safety reasons as judged by the investigator and/or AstraZeneca
- Severe non-compliance to protocol as judged by the investigator and/or AstraZeneca
- Incorrect enrollment or randomization of the patient.
- Development of exclusion criteria.
- Patient lost to follow-up

#### **3.3.5.2 Procedures for discontinuation**

If a patient discontinues participation or is withdrawn, the Clinical Monitor for the site must be contacted. The reason for, and date of, discontinuation for all patients from the study will be documented in source documents and the eCRF.

Parent or guardians who discontinue their child/ward should always be asked about the reason(s) for their discontinuation and about the presence of any adverse events. If possible, they should be seen and assessed by an investigator(s). Final visit procedures should be conducted. Adverse events should be followed up and any clinical assessment charts should be completed for the patient. All patients will be followed with a safety evaluation 14 days (+/- 2 days) after the final dose of study drug (Section 3.1.4).

### **3.3.5.3 Procedures for handling incorrect enrolled patients**

Patients not meeting the inclusion/exclusion criteria for a study should, under no circumstances, be enrolled into the study - there can be no exceptions to this rule. Where patients not meeting the study criteria are enrolled in error, incorrectly randomized, or where patients subsequently fail to meet the criteria for the study post enrollment, the patient should be discontinued and procedures from Section 3.3.5.2 should be followed.

## **3.4 Treatments**

### **3.4.1 Identity of investigational product and comparators**

A solution of esomeprazole sodium or placebo, which will be diluted with a sodium bicarbonate solution at the time of administration, will be used as investigational products in this study. The investigational products are described in Table 2.

Solution for oral use containing esomeprazole concentrate or placebo must be thawed, diluted and otherwise handled according to handling instructions that will be sent together with the investigational products.

The esomeprazole concentrate or placebo should be thawed at room temperature (15-25°C), protected from light. The thawing and diluting should be finished within 60 minutes. The study personnel will fill in the date and time that the concentration was thawed on the esomeprazole/placebo vial's label when the concentrate is removed from the freezer.

The sodium bicarbonate solution should be thawed at room temperature (15-25°C). The thawing will take approximately 60 minutes. After thawing the solution should be used for dilution within 8 hours. The study personnel will fill in the date and time that the sodium bicarbonate solution was thawed on the vial's label when the solution is removed from the freezer.

The diluted solution can be handled at room temperature (15-25°C), protected from light, and should be used within 60 minutes. The study personnel will fill in the date and time of dilution on the vial's label. For safety reasons, the reconstituted solution and remaining esomeprazole/placebo concentrate must be discarded immediately after use.

**Table 2 Identity of Investigational Product**

Investigational Product	Dosage form and strength	Container	Manufacturer	Formulation Numbera
Esomeprazole	Concentrate for oral solution 2.5 mg/mL	Vials of 10 mL containing 2 mL	AstraZeneca R&D Mölndal Sweden	H 1713-01-02
Placebo	Concentrate for oral solution	Vials of 10 mL containing 2 mL	AstraZeneca R&D Mölndal Sweden	H 1723-01-01
Sodium bicarbonate	Oral solution 23.3 mg/mL	Vials of 20 mL containing 9 mL	AstraZeneca R&D Mölndal Sweden	H 1714-01-02

aThe batch number will be recorded in the Study Master File and identified in the Clinical Pharmacology Study Report.

### 3.4.2 Doses and treatment regimens

The intention is to administer esomeprazole at 0.5 mg/kg/day. This dose will be given based on the patient's daily body weight, per NICU protocols.

The investigational product will be given once daily 30 minutes prior to a morning feeding during the treatment period. Study personnel will perform drug administration, by oral gavage (using a nasogastric or orogastric tube), or by nipple.

The esomeprazole concentrate and placebo solutions will be prepared by dilution of the concentrate with sodium bicarbonate solution prior to use. Dilution will be made into sodium bicarbonate vials. Each dose (0.5 mg/kg/day) will be administered in a volume of 2 mL/kg of liquid (= 0.5 mmol sodium bicarbonate and 0.5 mg esomeprazole/placebo of diluted solution per kg). This will be followed by administration of 5-10 mL of sterile water or formula.

### 3.4.3 Labelling

The packaging and labelling of study drug will be performed at Investigational Products, AstraZeneca R&D Mölndal, Sweden. Labelling will be in the local language for each country in accordance with Good Manufacturing Practice (GMP) and local regulatory requirements.

The vials containing esomeprazole or placebo will be labelled with at least the following information: sponsor's name and phone number, name of product, strength, dosage form, number of dosage units, study code and order reference, randomization code, period of use, eg, expiry date, and storage condition.

The vials containing sodium bicarbonate solution will be labelled with at least the following information: sponsor's name and phone number, name of product, strength, dosage form, number of dosage units, study code and order reference, period of use, eg, expiry date, storage condition, and dosage. The investigator's name and randomization code will be filled in on the label at the study site.

The esomeprazole/placebo concentrate will be packaged per patient in kits. The label on each of these vials and the outer box will contain pre-printed patient numbers according to the randomization list.

The sodium bicarbonate will be packaged in bulk. The label on the sodium bicarbonate vials will be a two-part label. One part will be permanently affixed to the vial and the other part will be a peel-off portion for insertion into the source documents. At the time of the dilution, the randomization code from the esomeprazole/placebo concentrate should be filled in on the label and on the tear-off part by study personnel.

All labels will be translated into local languages and each marketing company (MC) will be able to modify the text to meet local regulatory requirements.

#### **3.4.4 Storage**

All investigational products must be kept in a secure place under appropriate storage conditions (freezer, below -15°C). A description of the appropriate storage and shipment conditions are specified on the investigational product bottle label.

#### **3.4.5 Accountability**

Study drug will not be distributed to the medical institution until the contract is concluded between the medical institution and AstraZeneca. The study drug provided to the medical institution must only be used as directed by the study protocol. The Investigational Product Storage Manager is responsible for managing the study drug from receipt by the institution until the destruction of the study drug. All unused study drug should be destroyed at the local study site according to local standard operating procedures. AstraZeneca will provide the study documents 'Procedures for drug accountability' and 'Procedures for drug storage' which describe the specific requirements.

### **3.5 Method of assigning patients to treatment groups**

A preliminary identifying number (enrollment number) will be allocated to all patients at baseline, so that patients can be identified without making assumptions about their subsequent eligibility for the main study. Patients who do not meet the eligibility requirements for the treatment period will be considered screen failures and will keep their assigned identifying numbers.

Patient eligibility will be established before treatment randomization. Patients will be randomized strictly sequentially, as patients are eligible for randomization. If a patient discontinues from the study, the patient number will not be reused, and the patient will not be allowed to re-enter the study. If a number or a treatment is allocated incorrectly, no attempt should be made to remedy the error once study medication has been dispensed. The patient will continue with the allocated randomization code and corresponding clinical supplies. AstraZeneca or its designee should be notified as soon as the error is discovered.

### **3.6 Blinding and procedures for unblinding the study**

#### **3.6.1 Methods for ensuring blinding**

Patients who meet all study entry criteria and who provide written informed consent will be randomized in a blinded fashion into the treatment phase. Double-blind technique will be used in the treatment phase of the study. There will be no differences in the appearance between the vials of esomeprazole and placebo concentrate.

#### **3.6.2 Methods for unblinding the study**

Individual treatment codes, indicating the treatment randomization for each randomized patient, will be available to the investigator(s) or pharmacists at the study centre

The treatment code must not be broken except in medical emergencies when the appropriate management of the patient necessitates knowledge of the treatment randomization. The investigator(s) must document and report to AstraZeneca any breaking of the treatment code. AstraZeneca retains the right to break the code for SAEs that are unexpected and are suspected to be causally related to an investigational product and that potentially require expedited reporting to regulatory authorities.

Treatment codes will not be broken for the planned analyses of data until all decisions on the evaluability of the data from each individual patient have been made and documented.

### **3.7 Pre-study, concomitant and post-study treatment(s)**

Other medication, which is considered necessary for the patient's safety and well being, may be given at the discretion of the investigator(s) and reported to the Sponsor. The administration of all medication (including investigational products) must be recorded in the appropriate sections of the case report form (eCRF). No excluded medications (see Section 3.3.3) may be administered. The need for administration of any excluded medication may require withdrawal of the patient from the study or may render the patient's data un-evaluable.

### **3.8 Treatment compliance**

On all study days, study personnel will administer the investigational product.

## **4. MEASUREMENTS OF STUDY VARIABLES AND DEFINITIONS OF OUTCOME VARIABLES**

### **4.1 Primary variable**

The primary variable is change from baseline in the number of occurrences of symptoms of GERD, as observed from video recording, and GERD-related signs detected from cardiorespiratory monitoring.

- For other efficacy variables, see [Table 3](#).

## **4.2 Screening and demographic measurements**

Each patient will undergo a baseline assessment prior to study Day 1 (first day of study drug treatment). This will consist of:

- demographic data (date of birth, sex and race)
- medical history and documentation of normal ECG
- physical examination and vital signs - see [Table 5](#)
- laboratory screening (haematology, biochemistry and urinalysis)
- cardiorespiratory monitoring
- esophageal pH-monitoring
- intraluminal impedance monitoring
- video monitoring

Data listed above are to be recorded in the eCRF at the pre-entry visit.

## **4.3 Patient-Reported Outcomes (PROs)**

Not applicable

## **4.4 Health Economic measurements and variables**

Not applicable

## **4.5 Pharmacokinetic measurements and variables**

Not applicable

## **4.6 Efficacy and pharmacodynamic measurement and variables**

The study objectives and endpoints are summarized in [Table 3](#).

**Table 3 Study objectives and endpoints**

Objective	Endpoint	Summary statistic for analysis	Analysis method
Primary: to assess the difference between esomeprazole and placebo in the treatment of signs and symptoms of GERD as observed by 8-hour video and cardiorespiratory monitoring in neonatal patients	Primary: change from baseline in the number of occurrences of symptoms of GERD, as observed from video recording, and GERD-related signs detected from cardiorespiratory monitoring	Primary: mean change from baseline in symptomatic episodes by treatment group	Primary: ANCOVA, taking baseline number of episodes as a covariate, will be used for the treatment comparison

**Table 3 Study objectives and endpoints**

Objective	Endpoint	Summary statistic for analysis	Analysis method
Secondary: To assess the difference between esomeprazole and placebo in the treatment of symptomatic reflux episodes of GERD	Secondary: number of GERD-related signs (oxygen desaturation, apnea, bradycardia) at baseline and at end of study via clinical assessment charts	Secondary: (a) mean percentage of patients with each GERD-related sign (ie, #patients with event divided by #randomized in a treatment group), and separately for patients having at least one of the 3 signs, at baseline and end of study by treatment group  (b) mean percentage of apnea resolution rate (ie, #patients having apnea at baseline and having no apnea at the end of study divided by #patients having apnea at baseline) by treatment group (only considering patients having apnea at baseline)	Secondary: Descriptive statistics will be provided for the endpoints of interest
	Secondary: volume and frequency of vomiting episodes at baseline and at end of study via clinical assessment charts	Secondary: (a) mean percentage of patients with small/medium/large vomiting volume at baseline and at end of study by treatment group  (b) mean change from baseline in number of vomiting episodes by treatment group	
	Secondary: volume, frequency and duration of feeding at baseline and end of study via clinical assessment charts	Secondary: (a) mean volume per feeding and mean frequency of feeding by treatment group  (b) mean total feeding volume over 24 hours per kilogram by treatment group  (c) mean feeding duration by treatment group	
	Secondary: symptom severity recorded on the Physician's Global Assessment	Secondary: mean percentage of patients with no symptom (severity = none) at the end of study by baseline severity and by treatment group	

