### **3.1.3 Study Days 2-13 (or the day prior to the final study day)**

The investigational product will be administered approximately 30 minutes prior to a morning feeding on each study day as described in Section 3.4. Dosing will be based on the patient's daily bodyweight, per NICU standards.

Vital signs will be collected and weight and length will be measured.

Clinical assessment charts will be recorded on a continuous basis. The end of study clinical assessment chart will be recorded during a 24 hour period on the day prior to the final study day when the pH/impedance monitoring will be performed. This data will be summarized and recorded in the eCRF.

Adverse events (AEs), concomitant medications, and serious adverse events (SAEs) will be documented. The investigator or designee will assess these events on each study day.

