##### **4.6.6.2 Calculation or derivation of outcome variables**

Patients with severity of "None" from the Physician Global Assessment will be considered as having no GERD-related symptoms. Percentage of patients with no symptoms will be calculated, for baseline and end of study separately, by adding up patients with no symptoms divided by total number of patients with assessment data for a treatment group.

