### **6.3 Description of analysis sets**

There will be two analysis sets for the efficacy evaluation: the intent-to-treat (ITT) and the per-protocol (PP). The ITT set will include all randomized patients who take at least one dose of study medication and have valid efficacy measurements both at baseline and at the end of study. The ITT set will be considered the primary analysis set. The PP set includes all patients in the ITT set and those who do not have any major protocol violations. A detailed description of the PP population will be included in the SAP. The safety population will consist of all randomized patients taking at least one dose of study medication.

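### Table 3 divides charted apnea, bradycardia and desaturation by all randomised at end of study, so, read literally, an infant without a final chart counts as free of the sign

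*Protocol*

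**What the plan says.** Table 3 of the protocol, in the rows for the secondary objective on symptomatic reflux episodes, gives two summaries of the chart-based cardiorespiratory signs.

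- Summary (a) is the percentage of patients with each of oxygen desaturation, apnea and bradycardia, computed as "patients with event divided by #randomized in a treatment group", and also "separately for patients having at least one of the 3 signs, at baseline and end of study by treatment group".
- Summary (b) is apnea resolution: "patients having apnea at baseline and having no apnea at the end of study divided by #patients having apnea at baseline".

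The analysis attached to both is descriptive: "Descriptive statistics will be provided for the endpoints of interest".

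The end-of-study value rests on one chart. Section 3.1.3 says: "The end of study clinical assessment chart will be recorded during a 24 hour period on the day prior to the final study day". Section 4.6.4 adds that only this chart and the baseline chart are entered in the eCRF.

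Two other places define who is counted. For the Physician Global Assessment, Section 4.6.6.2 obtains the percentage without symptoms by "adding up patients with no symptoms divided by total number of patients with assessment data for a treatment group". Section 6.3 limits the ITT set, the primary efficacy set, to dosed patients who "have valid efficacy measurements both at baseline and at the end of study".

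**The concern.** The numerator of (a) requires a recorded event, while the denominator requires only randomisation. Where the final chart is absent, the formula classes the infant with those observed to be free of the sign, which is the favourable outcome. A fall from baseline can then appear through lost charts alone, and the arm that loses more charts looks better.

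Summary (b) leans the other way: an infant with baseline apnea and no final chart stays in the denominator without being able to count as resolved. Two figures in one cell, about the same infants and the same chart, thus carry opposite implied rules, and the Physician Global Assessment follows neither.

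Missing final charts are foreseeable. Table 1 marks the chart at baseline and on Days 1–13 but not in the study completion/early discontinuation column, so the duty of early discontinuers to undergo final procedures (Section 3.1.4) does not clearly secure one. Infants may also be discharged, dosed at home and readmitted for the final study day (Section 3.1), whereas study personnel record the chart, as events occur, over the preceding 24 hours.

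**Working it through.** **Inputs from the protocol.** The plan is for a minimum of 90 patients, to achieve 76 evaluable (synopsis); Section 3.1 expects about 30 randomised at each of 3 centres. The 76 is 2 × 38 from Section 6.5. The gap is 90 − 76 = 14, and 14/90 = 15.6%. The protocol states no expected percentage for the chart-based signs and no rate of missing charts, so there is no planned figure to reproduce for this endpoint.

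**Formula for (a).** Let N be the number randomised in an arm, m the share without a final chart, and p the proportion with the sign among those with a chart.

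Reported percentage = p × N(1 − m) / N = p × (1 − m).

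With patients who have a chart as the denominator, the result is p.

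**Size in one arm.** Assume p = 50%.

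- No charts missing: 50%, no bias.
- 5% missing: 0.50 × 0.95 = 47.5%.
- 15.6% missing: 0.50 × 76/90 = 42.2%. This is an upper illustration; it supposes that all 14 non-evaluable infants also lack a final chart.

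**Size between arms.** Assume 45 per arm, 14 missing charts in total, and the same observed rate p in both arms. The reported percentage in an arm with k missing charts is p × (45 − k)/45.

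| Observed p | 7 v 7 missing | 10 v 4 missing | Difference (points) | 12 v 2 missing | Difference (points) |
|---|---|---|---|---|---|
| 20% | 16.9% in both | 15.6% v 18.2% | 2.7 | 14.7% v 19.1% | 4.4 |
| 40% | 33.8% in both | 31.1% v 36.4% | 5.3 | 29.3% v 38.2% | 8.9 |
| 60% | 50.7% in both | 46.7% v 54.7% | 8.0 | 44.0% v 57.3% | 13.3 |

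Differences are taken before rounding. Each favours the arm with more missing charts. The protocol does not indicate which arm that would be.

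**Opposite conventions in (a) and (b).** Assume 45 randomised, 20 with apnea at baseline, 4 of those 20 without a final chart, and no new apnea among the rest.

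- If no charted infant changes, (a) falls from 20/45 = 44.4% to 16/45 = 35.6%, while (b) shows 0/20 = 0% resolved. Apnea appears to drop by about 9 points with nobody resolved.
- If half of the 16 charted infants resolve, (b) gives 8/20 = 40%, against 8/16 = 50% among those with a chart.

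The same four infants are free of apnea in (a) and unresolved in (b).

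**The case against.** The strongest reply has four parts.

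**The 90-to-76 gap is not a chart-missing rate.** A reader might infer that the planned attrition turns 50% into 42%. The protocol does not support that. Sections 3.1.6 and 4.6.1 tie evaluability to the 8-hour video. Charts are kept continuously, the end-of-study chart precedes the final monitoring, and Section 3.3.5.2 asks for charts to be completed at discontinuation. An infant can lack a usable final video and still have a chart. This part stands in full, so 15.6% serves only as an upper illustration.

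**Missing-data handling belongs to the SAP.** Section 6.1 does say so, and Table 3 does not state how an infant without a chart is classified. For an early stopper, the heading of Section 3.1.3 allows the day before that infant's own final day to serve as end of study. A SAP rule could therefore supply a status. The same caution applies to (b), where not resolved is inferred from the denominator. What remains is that the protocol itself fixes the denominator of (a) as all randomised. That is a stated choice and not an omission.

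**The ITT definition might govern.** If the number randomised is read as the number within the ITT set of Section 6.3, most of the problem goes. But the two wordings differ, and Section 6.3 does not say that valid measurements means this chart; an infant could qualify through the video.

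**The stakes are small.** Because apnea and bradycardia can be life-threatening, a reader might infer that an efficacy or safety conclusion is compromised. It is not. These summaries are descriptive. Table 3 and Section 6.4 compare the same signs by ANCOVA and chi-square using the video and cardiorespiratory monitoring, without this denominator. Charts are monitored for safety, and adverse events are collected separately. This part stands.

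**Conclusion.** The point holds in a conditional form. Taken as written, the end-of-study percentages in (a) are the observed rates multiplied by (1 − share missing), and unequal loss of charts creates a difference in favour of the arm that lost more. Apnea resolution leans the opposite way, and the Physician Global Assessment uses a third basis.

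The size depends on a quantity that the protocol does not give. At an assumed observed rate of 50%, the understatement is 2.5 points with 5% missing, 7.8 points in the upper illustration (50 − 42.2), and zero if every chart is present. The between-arm figures rest further on assumed arms of 45, 14 missing charts and the splits shown. No test, primary result or sample-size figure is affected. This is a denominator to correct in a secondary descriptive table.

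**What to change.** In Table 3:

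- For the sign percentages, replace the number randomised with the number of patients who have a chart at that time point, in line with Section 4.6.6.2.
- For apnea resolution, use patients with apnea at baseline and an end-of-study chart as the denominator.
- Show the number without a chart, per arm and time point, beside each percentage. A chart-based denominator can also mislead if infants lose charts because they deteriorate, so these counts need to be visible.

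A sensitivity table counting a missing chart as sign present is optional for a descriptive endpoint. The cost is a wording change in Table 3 and matching text in the SAP; no new data, visit or sample size is needed.
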